### 5.2. Full Analysis Set

The Full Analysis Set (FAS) will include all subjects who were consented and enrolled into this study (See Section 6.2 for definition of 'enrolled'). The FAS will be used to summarize major protocol deviations (PDs) and for all efficacy data listings.

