### 5.4. Evaluable Set

The ES will include all subjects in the FAS who have had at least a baseline and a Day 30 (Visit 3) post-treatment efficacy assessment. The ES will be used for all analyses of efficacy endpoints. This will be the primary analysis set for analysis of the primary endpoint.

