### 6.3. Missing Data

No imputation of missing data will be made for any of the outcome variables.

For the purpose of assigning treatment-emergent AEs (TEAEs), prior and concomitant medications, and prior and concomitant procedures, the followings rules will be applied for partial or missing start dates:

- If the day is missing, the first day of the given month will be used unless the month and year are the same as the month and year of enrollment, in which case the date of enrollment will be used.
- If the day and month are missing, the 1st of January will be used unless the year is the same as the year of enrollment, in which case the date of enrollment will be used.

- If the whole date is missing, the date of enrollment will be used.

Imputed dates will not be displayed in data listings.

Other dates will not be imputed.

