### 8.1. Primary Efficacy Endpoint and Analysis

The primary efficacy endpoint is the responder rate for lip fullness on the LFS2, which is defined as the proportion of subjects who show  $\geq 1$ -point improvement on the LFS2 compared to baseline assessment, at Day 30 after last treatment received.

The LFS2 is an Investigator assessment of overall lip fullness measured by a 5-point scale (see Table 4: Lip Fullness Scale 2 (LFS2)). The investigator will use the LFS2 to perform a live assessment of the subject at the visits specified in Table 2, Schedule of Visits and Procedures. Improvement will be calculated as post-treatment LFS2 score – baseline LFS2 score.

The LFS2 score at baseline and at Visits 3, 4, 5, and 6 as well as the improvement from baseline at all post-treatment visits and the responder rate for lip fullness on the LFS2 at Day 30 will be summarized using summary statistics for categorical data for the ES, and also for the PPS as a supportive analysis. LFS2 grades, scores and improvements from baseline will be listed for the FAS.

Table 4 Lip Fullness Scale 2 (LFS2)

Grade	Description	Score
Very Marked	Very significant red lip show, lower lip pout, and upper lip pout	4
Marked	Significant red lip show and lower lip pout	3
Moderate	Moderate red lip show with slight lower lip pout	2
Mild	Some red lip show; no lower lip pout	1
Minimal	Flat or nearly flat contour, minimal red lip show	0

Photographic images will be collected to capture the subject status at the time of the live assessments. Facial photographs will be captured prior to study treatments and immediately after. Additional images will be captured at the Day 30, Month 3, Month 6, Month 12 and any subsequent visits. Images will be used by the investigator and subject for the facial assessments. 3D photographs will also be taken for each subject to aid in facial assessments and measure the volume change in the lips. Photograph collection details will be listed only for the FAS.

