### 8.2. Secondary Efficacy Endpoint(s) and Analyses

#### 8.2.1. Oral Commissures Severity Scale (OCSS)

Change from baseline in OCSS will be determined at each post-treatment visit. The OCSS is an investigator assessment measured on a 4-point scale (see Table 5: Oral Commissure Severity Scale (OCSS)). The Investigator will use the OCSS to perform a live assessment of the subject at the visits specified in Table 2, Schedule of Visits and Procedures. Change from baseline in OCSS will be calculated as post-treatment OCSS score – baseline OCSS score.

The OCSS score at baseline and at Visits 3, 4, 5, and 6 as well as the change from baseline scores at all post-treatment visits will be summarized using summary statistics for categorical data for the ES. OCSS grades, scores and changes from baseline will be listed for the FAS.

Table 5 Oral Commissure Severity Scale (OCSS)

Grade	Description	Score
Severe	Very deep and/or long wrinkle or crease; frown at rest	3
Moderate	Moderately deep and/or long wrinkle or crease; downturned corners	2
Mild	Shallow, just perceptible wrinkle or crease; horizontal or slightly downturned corners	1
None	No wrinkle or fold; slight upturned corners	0

Photographic images will be collected to capture the subject status at the time of the live assessments as detailed in Section 8.1.

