#### 8.2.2. FACE-Q™ – Satisfaction with Lips Questionnaire

Subject's assessment of satisfaction with treatment of their lips as measured by the change from baseline in the FACE-Q™ Satisfaction with Lips questionnaire at all post-treatment visits. The subject will assess satisfaction using the 10 items on the Satisfaction with Lips questionnaire of the FACE-Q™ (see Protocol Appendix 5). The responses to the items will be combined to create a Rasch transformed scale score that ranges from 0 to 100. Change from baseline in FACE-Q™ scale score will be calculated as post-treatment FACE-Q™ scale score – baseline FACE-Q™ scale score.

The overall scale score at baseline and at Visits 3, 4, 5, and 6 as well as the change from baseline scores at all post-treatment visits will be summarized using summary statistics for continuous data for the ES. FACE-Q™ responses, scale scores and changes from baseline will be listed for the FAS.

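### Efficacy tables for Months 3, 6 and 12 leave out any treated subject who has no Day 30 assessment, although those endpoints do not use Day 30

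*SAP*

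**What the plan says.** SAP 5.4 limits the Evaluable Set (ES) to subjects in the Full Analysis Set (FAS) "who have had at least a baseline and a Day 30 (Visit 3) post-treatment efficacy assessment". It gives that set a wide scope: "The ES will be used for all analyses of efficacy endpoints". The opening of SAP 5 likewise makes the ES the primary set for the efficacy data.

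SAP 8.1 and 8.2 carry this to the later visits:

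- **LFS2:** "The LFS2 score at baseline and at Visits 3, 4, 5, and 6 as well as the improvement from baseline at all post-treatment visits" are tabulated on the ES, with the Per Protocol Set (PPS) as support.
- **OCSS:** "The OCSS score at baseline and at Visits 3, 4, 5, and 6", on the ES.
- **FACE-Q:** "The overall scale score at baseline and at Visits 3, 4, 5, and 6" is tabulated, and the "change from baseline scores at all post-treatment visits will be summarized using summary statistics for continuous data for the ES".
- **Both GAIS ratings, natural look and feel, smoothness, dynamic lip lines:** from Day 30 onward, on the ES.

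The table index (SAP 15) agrees. All eight efficacy parameters are labelled Evaluable Set, and the one additional efficacy table uses the PPS, which SAP 5.5 defines as a subset of the ES.

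The FAS has no Visit 3 condition, but no efficacy summary uses it: "The FAS will be used to summarize major protocol deviations (PDs) and for all efficacy data listings". On missing outcomes, SAP 6.3 says: "No imputation of missing data will be made for any of the outcome variables". Protocol 10.1.1 defines the ES in the same way but does not assign it to particular analyses; the SAP does that.

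**The concern.** A Visit 3 condition suits a Day 30 endpoint. It has no evident purpose at Months 3, 6 and 12. Changes in LFS2, OCSS and FACE-Q are taken from baseline, and Protocol Appendix 6 has GAIS judged against the baseline or pre-treatment image. None of these needs a Visit 3 value.

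A treated subject who missed Visit 3 but was rated at Months 3, 6 and 12 would be in none of the efficacy tables for those visits. The durability summaries would leave out observed data and depend on attendance at an earlier visit. If those who missed Visit 3 fared differently later, the tabulated rates would differ from the rates among everyone observed.

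The situation is foreseeable. Protocol 8.2.1 allows withdrawal of subjects who do not return, but it also has the investigator contact a subject who misses one or more visits and encourage attendance, so some may come back.

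There is also a small mismatch within the SAP. SAP 9.1 plots and correlates FACE-Q score by visit against injected volume on the Safety Set, which equals the FAS, while the FACE-Q table uses the ES. With even one such subject, figure and table for the same later visit would cover different people.

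**Working it through.** **Inputs.** From SAP 3.5: 60 subjects, an expected responder rate of 80%, a 95% margin of error of 10%, and an expectation of almost no dropout at Day 30, without a number. The documents give no figure for subjects who miss Visit 3 and return later. I assume k of 60, with k from 0 to 6 and no other loss. I borrow the 80% rate for a later-visit proportion purely as an illustration.

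**Step 1: the plan's own figure.** Half-width = 1.96 × √(p(1 − p)/n) = 1.96 × √(0.80 × 0.20/60) = 0.1012, or 10.1%. This reproduces the stated 10%.

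**Step 2: precision at a later visit under the ES rule.** The same formula with n = 60 − k:

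| k | n in the ES table | Share omitted (k/60) | Half-width |
|---|---|---|---|
| 0 | 60 | 0% | 10.1% |
| 1 | 59 | 1.7% | 10.2% |
| 3 | 57 | 5.0% | 10.4% |
| 6 | 54 | 10.0% | 10.7% |

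**Step 3: possible shift in a later-visit rate.** Let ES subjects respond at 80% and the omitted subjects at rate q. The rate among all observed is ((60 − k) × 0.80 + k × q)/60. The ES table therefore differs from it by k × (0.80 − q)/60.

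| k | All observed, q = 0% | All observed, q = 100% | ES minus all observed |
|---|---|---|---|
| 1 | 78.7% | 80.3% | +1.3 to −0.3 points |
| 3 | 76.0% | 81.0% | +4.0 to −1.0 points |
| 6 | 72.0% | 82.0% | +8.0 to −2.0 points |

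A less extreme case: k = 3 and a 30-point difference between omitted and retained subjects gives 3/60 × 30 = 1.5 points. With k = 0, or with q equal to 80%, there is no shift.

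**Step 4: the Day 30 primary.** Because outcomes are not imputed, a subject with no Visit 3 assessment has no Day 30 LFS2 result under any analysis set. The Visit 3 condition therefore removes nothing further from the Day 30 responder table.

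**The case against.** A reader might infer that valid ratings are thrown away. The documents do not support that. Every efficacy rating is listed for the FAS, and FACE-Q scores also reach the Safety Set scatter plots and correlations. The exclusion is open too: SAP 7.1 reports the numbers in each analysis set with reasons for exclusion, backed by Table 14.1.2.2 and Listing 16.2.3.2. This stands: the data are omitted from summary tables, not lost.

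The affected group is also narrow. SAP 3.8.2 lets an unscheduled visit replace a missed scheduled one. SAP 5.4 names no instrument, so one completed Visit 3 scale may be enough to qualify. A subject who leaves before Day 30 and does not return has no later data under either rule. The expectation of almost no dropout at Day 30 also suggests small numbers, though it concerns dropout and not single missed visits. All of this stands and limits the size.

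The strongest argument for the rule is that a single prespecified set lets durability be read in the same subjects who supply the Day 30 result. That is a legitimate preference and not a contradiction in the plan, but the gain is weak. The ES requires attendance at Visit 3 and not at Visits 4 to 6, so without imputation n still varies across the later visits and no fixed cohort results.

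Finally, if attendance at Visit 3 is unrelated to later outcome, no bias is expected and only a little precision goes. The documents give no reason to think it related, so the shifts in step 3 are possibilities and not predictions.

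**Conclusion.** The point holds as a minor one. As written, a treated subject with no Visit 3 assessment and no replacing visit is left out of every efficacy summary table at Visits 4, 5 and 6, and the documents give no reason for conditioning those tables on Visit 3.

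The size depends on a count the documents do not give. With none there is no effect. For an assumed 1 to 6 of 60, the half-width at 80% rises from 10.1% to between 10.2% and 10.7%. A later-visit rate could shift by about 1 to 8 points, but only if every omitted subject failed; a 30-point difference with 3 omitted subjects gives 1.5 points. Against a planned margin of 10 points in a descriptive study, that is small. One omitted subject could weigh more in the small cells that SAP 6.6 creates by gender, age group, baseline LFS2, phototype and site.

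It would be going too far to conclude that the primary result is affected or that the durability results are known to be biased. The first is ruled out by the lack of imputation, and the second would need both a count and a link between attendance and outcome that the documents do not supply.

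**What to change.** Amend SAP 5 (opening statement), 5.4, 8.1 and 8.2 along these lines:

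> The ES is used for the Day 30 (Visit 3) efficacy summaries. Efficacy summaries at Visits 4, 5 and 6 include all FAS subjects with a baseline, where the endpoint has one, and a value at that visit. The number of subjects is shown for each visit.

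Update the analysis-set labels in the table index (SAP 15) to match. Protocol 10.5.2 leaves the other efficacy analyses to the SAP and Protocol 10.8 provides for changes by SAP amendment, so the protocol's definition of the ES can stay as it is. The Day 30 primary analysis does not change.

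The cost is a short amendment and relabelled tables. The downside is that n, and the subjects behind it, may differ between Day 30 and the later visits, which is why n should be shown per visit.

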### 5.5. Per Protocol Set

The Per Protocol Set (PPS) will include all subjects in the ES who had not had any major protocol deviations. The PPS will be used to corroborate the results from the ES for the primary endpoint. Criteria for exclusion from the PPS will include the following important PDs:

- Use of a prohibited medication.
- Use of prohibited concomitant procedures.
- Violation of key inclusion or exclusion criteria.
- Violation of follow-up, or significant deviation from defined visit windows.

Subjects will be assigned to the PPS by Allergan by reviewing PDs as detailed in Section 5.6.

### 5.6. Protocol Deviations

PDs will be captured in the clinical trial management system (CTMS). These will be reviewed by Allergan throughout the study to determine whether each PD is major or minor with respect to inclusion in the PPS. All PDs will be listed for the Screened Set and major PDs will be summarized by deviation type using summary statistics for categorical data for the FAS.

## 6. General Aspects for Statistical Analysis

### 6.1. General Methods

- All tables, figures, listings (TFLs), and statistical analyses will be generated using SAS for Windows, Release 9.4 or higher (SAS Institute Inc., Cary, NC, USA).
- Unless otherwise specified, summaries will be presented for each gender and overall.
- Continuous variables will be summarized using the number of observations (n), mean, standard deviation (SD), median, minimum, and maximum. Categorical variables will be summarized using n and percentage of subjects.
- All relevant subject data will be included in listings. All subjects entered into the database will be included in subject data listings.

### 6.2. Key Definitions

A subject is considered 'entered' into the study after the subject has signed the Informed Consent Form (ICF) and a subject number has been assigned.

A subject is considered 'enrolled' after confirmation of participation eligibility and treatment with the investigational product Juvéderm® VOLIFT™ with Lidocaine has occurred during the study.

Study treatment is defined as initial or touch-up treatment with Juvéderm® VOLIFT™ with Lidocaine.

Baseline is defined as the latest assessment prior to any study treatments for each subject.

Study day will be calculated as (date of event or assessment)-(date of first filler treatment)+1 if the event or assessment was on or after the date of the first filler treatment, and as (date of event or assessment)-(date of first filler treatment) if the event or assessment was before the date of the first filler treatment. The day of first filler treatment is Study Day 1 (Visit 1). If a touch-up treatment is administered, Visits 3, 4, and 5 will be 14 days +/- 3 days later than the visit label and window, e.g. the study day for an assessment at Visit 3 (Day 30) could be 44 +/- 10, rather than 30 +/- 7.

End of study is the last clinical visit an enrolled subject has in this study. For subjects who complete this study, the end of study visit will be their Visit 5; for subjects who drop out early, they will be asked to come back for the last clinical visit for end of study data collection.

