**PROTOCOL SUMMARY**

Sponsor: Allergan Pharmaceuticals International Limited, [name]
	
Investigational Products: Juvéderm® VOLIFT™ with Lidocaine
	
Developmental Phase: Phase IV, Post-marketing

Title of Study: LIPS: Prospective, open-label study to evaluate the effectiveness of Juvéderm® VOLIFT™ with Lidocaine for lip augmentation
		

Protocol Number: CMO-MA-FAS-0512
		

Number of Subjects: 60 subjects
		

Indication: Lip augmentation
		

Primary Study Objective: To evaluate the effectiveness of Juvéderm® VOLIFT™ with Lidocaine for lip augmentation.
 
Secondary Study Objectives: To quantify the Investigators’ and subject’s assessment of aesthetic improvement of their lips.
		

Methodology: This is a prospective, open-label, multi-centre, interventional, medical device, post-marketing study. Each subject will act as his/her own control. Eligible subjects will undergo treatment with Juvéderm® VOLIFT™ with Lidocaine injected into the lips for lip augmentation.
 
All subjects will sign an informed consent form, and begin at the Screening Visit (V0). Filler treatment (Juvéderm® VOLIFT™ with Lidocaine) will be performed at V1 (Initial Treatment visit) and data will be collected at this visit for all relevant parameters as per the Schedule of Study Procedures, Treatments and Assessments (Table 1.1). Fourteen days after the initial treatment, subjects will return to the clinic and the Investigator will assess whether a Touch-up treatment is to be performed at this visit (V2). Follow-up visits will occur at V3, V4, V5, and V6 at 1, 3, 6, 12 months after the last treatment.
		

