## 10 STATISTICAL METHODS

### 10.1 GENERAL STATISTICAL CONSIDERATIONS

A brief summary of the general statistical analysis methods is provided below; full details will be provided in a separate Statistical Analysis Plan (SAP), which will be finalized prior to database lock.

Data will be summarized using descriptive statistics (number of observations (n), mean, standard deviation (SD), median, minimum, and maximum for continuous variables; and n and percent for categorical variables).

Baseline is defined as the latest assessment prior to any study treatments for each subject. End of study is the last clinical visit an enrolled subject has in this study. For subjects who complete this study, the end of study visit will be their V5 visit; for subjects who drop out early, they will be asked to come back for the last clinical visit for end of study data collection.

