### **2.2. Timings of Analyses**

The primary analysis of safety and efficacy is planned after all subjects complete the final study visit or terminate early from the study. An interim analysis will be performed when all patients complete their 6 months visit (or discontinue early).

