#### **3.3. Brief Description**

This is a prospective, open-label, multi-center, interventional, medical device, post-marketing study evaluating the effectiveness of Juvéderm® VOLIFT™ with Lidocaine for lip augmentation. Subjects will attend up to 7 visits: Screening, Initial Treatment, Day 14 (touch-up, if required), Day 30, Month 3, Month 6, and Month 12 (study exit; see Figure 1). 60 subjects will be enrolled.

Eligible subjects will undergo treatment with Juvéderm® VOLIFT™ with Lidocaine administered via injection for enhancement as per the current directions for use (DFU)

[figure not shown]
[figure not shown]
[figure not shown]

Figure 1 Overall Study Design

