## 7. Demographic, Other Baseline Characteristics and Medication

### 7.1. Subject Disposition and Withdrawals

The number of subjects entered and the number and percentage of subjects enrolled, completed and discontinued, together with the reasons for discontinuation will be summarized for the Screened Set. Disposition details and inclusion and exclusion criteria not met will be listed for the Screened Set.

The number and percentage of subjects included in, and reasons for exclusion from, each of the analysis sets will be presented for the Screened Set. Exclusions from analysis sets will be listed for the Screened Set.

No formal statistical testing will be carried out on these data.

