## **10. Interim Analyses**

An interim analysis will be performed when all patients complete their 6 months visit (or discontinue early). All TFLs detailed in Sections 15 to 17 will be provided using all data available at the time.

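### Completers' end of study is given as Visit 5 (Month 6) although study exit is Visit 6 (Month 12), so completion can be read two ways; the total-volume displays also need a stated cut-off

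*SAP*

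**What the plan says.** **End of study.** SAP 6.2 gives two rules side by side. The general one is "End of study is the last clinical visit an enrolled subject has in this study". The next sentence says "For subjects who complete this study, the end of study visit will be their Visit 5". Protocol 10.1 carries the same pair: "For subjects who complete this study, the end of study visit will be their V5 visit".

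**Visit plan.** The Protocol Summary states "Follow-up visits will occur at V3, V4, V5, and V6 at 1, 3, 6, 12 months after the last treatment". SAP 3.3 lists the last visit as "Month 12 (study exit; see Figure 1", and Protocol section 3 also names Month 12 as study exit.

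**Analyses and disposition.** SAP 2.2 states "The primary analysis of safety and efficacy is planned after all subjects complete the final study visit or terminate early from the study" and places an interim at Month 6. For that interim, SAP 10 states "All TFLs detailed in Sections 15 to 17 will be provided using all data available at the time". SAP 7.1 will summarise "the number and percentage of subjects enrolled, completed and discontinued, together with the reasons for discontinuation" (Table 14.1.1). Protocol 8.2 requires the date and reason of any withdrawal to be recorded, and Protocol 6.2.9 requires refusal of the extension after Month 6 to be recorded.

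**Volume.** SAP 9.1 describes exposure at Visit 1, Visit 2 (touch-up) and Visit 6 (optional retreatment), then an overall total per subject with no exclusion. That total is set against adverse events (Table 14.3.4.4) and correlated with FACE-Q at each visit (Figure 14.3.4.5). SAP 6.2 limits study treatment to the initial and touch-up injections, while Protocol 7.1.5 and SAP 7.4 list the Month 12 retreatment among study treatments.

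**The concern.** The end-of-study sentence is a stated definition, and it is wrong as written for anyone who enters the extension. The visible SAP gives no other definition of *completed*. A programmer could apply either Visit 5 or Visit 6, and the same row of Table 14.1.1 could mean one thing at the interim and another at the final analysis, because all outputs are produced at both.

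The volume question is one of time order. If the total includes the Visit 6 retreatment, Figure 14.3.4.5 relates satisfaction scores to product injected after they were given. At the interim, Visit 6 volume exists only for subjects already at Month 12. The Day 30, Month 3 and Month 6 coefficients could then change between interim and final with no new score at those visits.

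**Working it through.** **1. Visit numbers (Protocol Summary).** Visits 3, 4, 5 and 6 are at 1, 3, 6 and 12 months after the last treatment. So Visit 5 is Month 6 and Visit 6 is Month 12. The Visit 5 rule leaves out 1 of 4 follow-up visits and 12 − 6 = 6 of 12 follow-up months.

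**2. The rules applied to three subjects.**

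| Subject | Last-clinical-visit rule | Visit 5 rule | Month 12 exit |
|---|---|---|---|
| Attends Visit 6 | Visit 6 | Visit 5 | completed at Visit 6 |
| Attends Visit 5, declines the extension | Visit 5 | Visit 5 | not classified |
| Consents to the extension, has no clinic visit after Visit 5, leaves before Visit 6 | Visit 5 | Visit 5, can be read as completed | discontinued |

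The Visit 5 rule fits only the second subject. For the first, two adjacent sentences name different visits. For the third, the completion status itself can differ.

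**3. Size for the disposition table.** With 60 treated (SAP 3.4), each such subject moves the completion rate by 1/60 = 1.7 percentage points. The documents give no rate of refusal or loss after Month 6, so the range below is an assumption. If all 60 reach Visit 5 and 100, 90, 80, 70 or 50% of them reach Visit 6, the Visit 5 reading gives 60/60 (100%) each time. The Visit 6 reading gives 60, 54, 48, 42 or 30 of 60 (100, 90, 80, 70 or 50%). The gap runs from 0 to 50 points and includes subjects who decline the extension.

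**4. Other six-month text.**
- The Protocol Summary gives participation of about 6 months. With up to 14 days of screening (Protocol 6.1.3), the visit plan gives 14 + 365 = 379 days without touch-up and 14 + 14 + 365 = 393 days with it.
- Protocol 6.2.9 ties the early-exit visit to Month 6.
- SAP 6.2 applies the touch-up shift to Visits 3, 4 and 5. The note to Protocol Figure 3.1 also includes Visit 6.

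**5. Order of volume and score.** FACE-Q is summarised at baseline and Visits 3 to 6 (SAP 8.2.2). Visits 3, 4 and 5 precede Visit 6. Protocol section 3 puts the Month 12 assessments before the retreatment offer. On that order all 4 post-treatment scores precede the Visit 6 injection, and none can reflect it.

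**6. What does not move.** The plan's one sample-size figure is a 10% margin for an 80% responder rate with 60 subjects: 1.96 × √(0.8 × 0.2 / 60) = 0.101. It reproduces and does not depend on this point. The primary endpoint is read at Day 30, and the Evaluable Set needs only a baseline and a Day 30 assessment.

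**The case against.** **Completion.** The Visit 5 sentence presupposes completion and does not define it. In the visible text no endpoint, analysis set or missing-data rule uses end of study. A subject who leaves before Visit 6 has a recorded withdrawal, so counting that subject as completed would mean overriding a recorded fact. The table shells and the section on consent to the extension are redacted and may already separate the groups. This stands to the extent that misclassification is possible, not certain, and that no data are lost. It does not remove a visible definition that contradicts the visible study exit.

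**Volume.** The SAP's own definition of study treatment leaves retreatment out. A display of volume against FACE-Q by visit could mean volume received up to that visit, and the figure shell is redacted. This also stands: inclusion of Visit 6 is the natural reading of SAP 9.1, but the SAP does not settle it.

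**A stronger reading.** A reader might infer that collection of non-serious events stops at the visit where retreatment is injected. Protocol Table 9.1 ends that collection at the last subject visit, and Protocol 9.1.7 and SAP 9.5 name the diary only for initial and touch-up treatment. The documents do not establish the inference:
- Protocol 7.1.6 allows for visits after Month 12.
- Protocol 7.1.7 does not limit the diary to the first two injections.
- Protocol 9.1.7 passes injection site reactions to product surveillance on a condition set 30 days after the last study visit. This can be read as keeping earlier ones within the study.
- Protocol 6.2.8 has events recorded at any unscheduled return.
- Protocol 9.3 covers serious events, device deficiencies and incidents until 30 days after the last treatment or visit, whichever is later.

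**Size of the correlation effect.** Any figure needs an assumed retreatment rate and volume, which the documents do not give, so none is used here to show importance.

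**Conclusion.** The end-of-study wording is wrong for subjects who enter the extension and should be corrected in both documents. It permits, but does not force, a subject lost between Visits 5 and 6 to be counted as completed, at 1.7 points per subject among 60. Confidence in the textual conflict is high.

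The volume point is secondary and held with lower confidence. It rests on the natural reading of SAP 9.1 and on the Month 12 order in Protocol section 3. If both hold, the Visit 6 part of the total has no bearing on any FACE-Q score in Figure 14.3.4.5.

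Overall severity is minor. Only descriptive outputs are affected. Nothing here shows that post-retreatment events go uncollected.

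**What to change.** **End of study (SAP 6.2, Protocol 10.1).** Make Visit 6 the end-of-study visit for subjects who consent to the extension. In Table 14.1.1 give separate rows for Month 6 completion, extension declined, and Month 12 completion or discontinuation with reasons. Use the same rows at interim and final. Align the participation time in the Protocol Summary, the early-exit text in Protocol 6.2.9 and the touch-up shift in SAP 6.2 with the 12-month plan.

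**Volume (SAP 9.1).** State that Figure 14.3.4.5 uses volume given before the assessment, which is Visit 1 plus Visit 2 for Visits 3 to 6. In Table 14.3.4.4 compare Visit 1 plus Visit 2 volume by treatment-emergent events with onset before any Visit 6 retreatment. Restricting the volume alone would leave later events in the table without the injection that preceded them. Report Visit 6 volume separately, and list any events after it separately.

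**Reconcile.** The sponsor should reconcile the passages on event and diary collection (Protocol 6.2.8, 7.1.6, 7.1.7, 9.1.7, Table 9.1 and 9.3; SAP 9.5) and on study treatment (SAP 6.2 and 7.4; Protocol 7.1.5) with the Visit 6 retreatment. No collection window is proposed, and no view is taken on retreatment.

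**Cost.** The SAP needs a few sentences, one set of disposition rows, one volume variable and an onset cut-off. No new data are needed. The protocol part is text alignment. If it led to a revised consent form, Protocol 11.6 would require ethics approval and re-signing, so it can wait for the next amendment while the SAP is corrected now.
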